## Statistical Design and Power

Statistical Analysis. The College of Health Sciences supports the effort of a biostatistician through the Office of Research to provide dedicated support to funded investigators. All statistical analyses will be performed using SAS© 9.4 (SAS institute, Cary NC). The sample size calculations herein have been performed with the assistance of the biostatistician. We used 4 main outcomes to determine sample size: cross sectional area (CSA), myofibrillar protein synthesis (MyoKsyn), extracellular vesicle (EV) number and mRNA levels of Rab27. These outcomes were also measured in the pilot study we performed with 6 subjects and the variance and expected differences were based on the data from the pilot study. See Table below.

% change	EV number	CSA	MyoKsyn	Rab27 mRNA
Pilot study data	0.29	6.1	36	116
Expected μ₁-μ₂	0.29	10	70	150
Standard Deviation, σ	0.294	11	76	170
Effect Size, $\delta =  \mu_1 - \mu_2 /\sigma$	0.99	0.91	0.92	0.88
n per Group	18	21	19	22

From this sample size analysis we decided to use n=22 per group, because it would give us the power to determine differences in the mRNA expression of EV biogenesis markers as well as enough power to detect changes in muscle size and protein synthesis. To determine statistically significant differences between the groups we will use a Two Way ANOVA to determine effects of ULLS and massage. Holm Sidak posthoc tests will be performed in case significance is seen with the ANOVA. We will use an unpaired t-test to test for cross over effect (UM versus UC left nonmassaged limb).

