Describe the characteristics of the subject population, including age range, gender, ethnic background and health status. Identify the criteria for inclusion and exclusion.

Provide the following information:

- A description of the subject selection criteria and rationale for selection in terms of the scientific objectives and proposed study design;
- A compelling rationale for proposed exclusion of any sex/gender or racial/ethnic group;
- Justification for the inclusion of vulnerable groups such as children, prisoners, adults with impaired consent capacity, or others who may be vulnerable to coercion or undue influence.

Please consider these resources:

- [NIH Diversity Policy](#)
- [FDA Diversity Guidance](#)

This study will include 70 subjects of either gender. Subjects will be randomly assigned to the following groups: (1) normal weight-bearing, massage (WB-M), (2) normal weight bearing, no massage (WB-C) (3) ULLS, no massage (U-C), and (4) ULLS, massage (U-M). Inclusion criteria are as follows: healthy subjects aged 18-30 years. Exclusion criteria include:

- BMI over 27
- Have current lower extremity musculoskeletal injuries
- Have had previous lower extremity surgeries or injury
- Activities of daily living require long periods of standing or driving a manual transmission car.
- Evidence or signs and symptoms of metabolic syndrome or disorder (diagnosis of diabetes or insulin resistance, elevated BP, high fasting blood sugar, abnormal cholesterol or triglyceride levels).
- Thyroid disorder
- Acute or chronic infections
- Use of systemic steroids, anabolic steroids, or growth hormone
- Are currently pregnant
- Have a family history of bleeding problems ("free bleeder"), as evidence by:
 - o unexplained nosebleeds (epistaxis)
 - o excessive or prolonged menstrual blood flow (menorrhagia)
 - o prolonged bleeding after minor cuts, dental procedures, tooth brushing or flossing, or trauma
- Are using medications that increase the risk of bleeding (unless it can be safely stopped):
 - o Aspirin
 - o Clopidogrel
 - o non-steroidal anti-inflammatory drugs
 - o any anticoagulation therapy (warfarin or heparin)
- Are allergic to Betadine or Xylocaine HCl.
- Any other condition or events considered exclusionary by the PI and /or physician, such as non-compliance

Attachments

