Indicate the targeted/planned enrollment of the following members of minority groups and their subpopulations. Possible demographic sources: [Census Regional Analyst Edition](#), [Kentucky Race/Ethnic Table](#), [Kentucky Population Data](#).
(Please note: The IRB will expect this information to be reported at Continuation Review time for Pre-2019 FDA-regulated Expedited review and Full review applications):

| Participant Demographics | | | | |
|---|----------------------|----------------------|----------------------|----------------------|
| | Cisgender Man ⓘ | Cisgender Woman ⓘ | TGNB/TGE ⓘ | Unknown/Not Reported |
| American Indian/Alaskan Native: |  |  |  |  |
| Asian: | 3 | 3 |  |  |
| Black/African American: | 9 | 9 |  |  |
| Latinx: | 2 | 2 |  |  |
| Native Hawaiian/Pacific Islander: |  |  |  |  |
| White: | 56 | 56 |  |  |
| American Arab/Middle Eastern/North African: |  |  |  |  |
| Indigenous People Around |  |  |  |  |

| | | | | |
|--------------------------|--|--|--|--|
| the World: | | | | |
| More than One | | | | |
| Race: | | | | |
| Unknown or Not Reported: | | | | |

If unknown, please explain why:

Indicate the categories of subjects and controls to be included in the study. You may be required to complete additional forms depending on the subject categories which apply to your research. If the study does not involve direct intervention or direct interaction with subjects, (e.g., record-review research, outcomes registries), do not check populations which the research does not specifically target. For example: a large record review of a diverse population may incidentally include a prisoner or an international citizen, but you should not check those categories if the focus of the study has nothing to do with that status.

Check All That Apply (at least one item must be selected)

ADDITIONAL INFORMATION:

- Children (individuals under age 18)
- Wards of the State (Children)
- Emancipated Minors
- Students
- College of Medicine Students

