The unilateral lower limb suspension (ULLS) method has been recently developed to mimic the 0-g conditions in space and assist in assessing the efficacy of interventions to combat muscle atrophy and facilitating in-vivo muscle performance studies.¹⁰ ULLS has been shown to mimic bed rest and is a valid technique.¹¹ Just as muscle tissue responds to loading, muscle responds to unloading as well. Unloading a muscle can result in muscle atrophy at a weekly rate of about 2.5% particularly for knee extensors.¹⁰ Short term ULLS (10-16 days) doesn't seem to result in large macroscopic changes in muscle size or CSA but individual muscle fiber size has been shown to decrease at a weekly rate that varies between 3-8% across different studies.¹⁰ In specific studies, increased markers for muscle proteolysis were found after 3 days of ULLS¹⁰ and protein synthesis rate appeared to decrease after 10 days of ULLS.⁹ ULLS is a well-accepted model for disuse-induced muscle atrophy.¹⁰ There are few systemic or general deconditioning effects that have been discovered from incorporating ULLS into research procedures.¹⁰ Overall, ULLS has been shown to be a valid, practical, and cost-effective method to induce atrophy and study the effects on skeletal muscle.¹⁰

Objectives

List your research objectives. Please include a summary of intended research objectives in the box below.

The objective of this study is to determine if an optimal load of massage induces protein synthesis and increases cross sectional area

in unperturbed or atrophied human skeletal muscle tissue. In addition, we will determine whether an optimal load induces muscle damage and causes a satellite cell response in control and atrophied human skeletal muscle tissue while also examining extracellular vesicles and their possible role in a physiological phenomenon called the crossover effect. We hypothesize that 15 min of massage with a 35 N load for 4 days will not induce muscle damage but will still cause an increase of satellite cells, extracellular vesicles, as well as in cross sectional area and protein synthesis.

Study Design

Describe and explain the study design (e.g., observational, secondary analysis, single/double blind, parallel, crossover, deception, etc.).

- *Clinical Research*: Indicate whether subjects will be randomized and whether subjects will receive any placebo.

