This study is designed as a randomized control trial. Figure 1 shows the time line for the study. There will be four groups of subjects, (1) normal weight-bearing with massage (WB-M), (2) normal weight bearing without massage (WB-C) (3) ULLS, no massage (control, U-C), and (4) ULLS with massage (U-M). We expect to recruit 140 subjects to in order in fully enroll 128 (32 per group, n = 3 per group for attrition). For measurement of protein synthesis, participants will ingest three 50 mL doses of heavy water (2H2O) for the first two days and the dose will decrease to two 50 mL doses per day (a total of 1000 mL of heavy water for each subject over the course of the trial). 3-4 blood draws will be taken on days 2, 5, 7, and 9 and each will be drawn at the same time each day. Subjects in U-C and U-M groups will have their left leg immobilized and suspended using a hinged knee brace. Those immobilized will be required to wear the brace and use crutches at all times, except while showering and sleeping. Immobilization will begin on day 2 and will continue until the end of the study (day 9). Members of the research team will use a custom-made device to massage the quadriceps region of subjects' left leg and leave the right leg unaffected in the WB-M and U-M groups. Massage treatments will begin on day 3 and will take place every other day (day 5, 7, 9) until the end of the study. A baseline muscle biopsy of the vastus lateralis will be taken from the right leg on day 2, prior to the first massage. Muscle biopsies will then be taken from both legs 4-6 hours after the last massage on day 9, and the muscle tissue will be frozen for further examination. (See Figure 1). Sham treatment for the WB-C and U-C groups will include us touching the skin using a light brushing technique.

For the weight bearing groups as comparison groups, they will also have to drink deuterium oxide heavy water over 9 days which is associated with 3-4 blood draws but will not have to wear a brace or use crutches. Weight bearing control groups will only have one biopsy taken on day 9 while weight bearing massage groups will have two biopsies taken (day 2- right leg, and day 9- left massaged leg). This will still allow for effective comparison between groups and will reduce burden on these participants. We will enroll the weight bearing groups after immobilization groups to ensure that those interested in the study will not drop out after possible randomization into the immobilization group.

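### The SAP says its expected differences came from the 6-subject pilot, but three of the four are set above the pilot row without a reason, and n=22 per group rests on the raised values

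*SAP*

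**What the plan says.** The SAP (Statistical Design and Power) bases the sample size on EV number, CSA, MyoKsyn and Rab27 mRNA, all measured in a pilot of 6 subjects, and says that "the variance and expected differences were based on the data from the pilot study". The table beneath, headed as percentage change, has a row of pilot data and a separate row of expected differences between two means, then the SD, effect size and n per group. The SAP settles on 22 per group, citing power for the mRNA markers "as well as enough power to detect changes in muscle size and protein synthesis". It states no alpha, sidedness or target power.

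For the analysis, "we will use a Two Way ANOVA to determine effects of ULLS and massage", with Holm-Sidak post hoc comparisons. Separately, "We will use an unpaired t-test to test for cross over effect". The protocol's Objectives section asks about massage "in unperturbed or atrophied human skeletal muscle tissue".

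The protocol gives other sample sizes. Its Study Design section expects to recruit 140 and "fully enroll 128 (32 per group, n = 3 per group for attrition". Its description of the subject population says "This study will include 70 subjects of either gender". The planned enrolment table in the same section lists 70 men and 70 women.

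**The concern.** A reader who takes the SAP at its word will believe the trial was sized on effects seen in the pilot. For three of the four outcomes it was not: the values used are larger, and neither document says why. This matters most for CSA and protein synthesis, which the protocol's objective names first and for which the SAP claims adequate power without giving a figure. If either result is null, readers will look to that claim to judge whether an effect of the size seen in the pilot could have been missed. As written they cannot tell, because the claim depends on which differences, and which n, were meant.

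**Working it through.** **Inputs** (SAP table):

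| | EV number | CSA | MyoKsyn | Rab27 mRNA |
|---|---|---|---|---|
| Pilot row | 0.29 | 6.1 | 36 | 116 |
| Expected difference | 0.29 | 10 | 70 | 150 |
| SD | 0.294 | 11 | 76 | 170 |
| Tabled n per group | 18 | 21 | 19 | 22 |

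Assumed, because the SAP does not state them: two-sided alpha of 5%, target power of 80%, two equal groups, t-test.

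**Step 1: reproduce the plan.** Effect size d = expected difference / SD:
- EV number: 0.29/0.294 = 0.99
- CSA: 10/11 = 0.91
- MyoKsyn: 70/76 = 0.92
- Rab27: 150/170 = 0.88

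These match the table. The n per group for 80% power (noncentral t) is 17.15, 20.002, 19.51 and 21.17, which round up to 18, 21, 20 and 22 against the tabled 18, 21, 19 and 22. So the table is a two-group calculation on the expected-difference row. The assumed settings fit but are not uniquely identified: one-sided 5% with 90% power gives similar numbers (18, 21, 21, 22 by the normal approximation).

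**Step 2: compare the two rows.** Expected / pilot:
- EV number: 0.29/0.29 = 1.00
- CSA: 10/6.1 = 1.64
- MyoKsyn: 70/36 = 1.94
- Rab27: 150/116 = 1.29

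Rounding does not explain the last three. This step needs no assumption.

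**Step 3: power at each row, if the pilot row is a between-group difference.** Noncentrality = d × √(n/2), with 2n − 2 degrees of freedom. At the pilot values d is 6.1/11 = 0.555, 36/76 = 0.474 and 116/170 = 0.682. For CSA at n=22, for example, noncentrality is 0.555 × √11 = 1.84 at the pilot value and 0.909 × √11 = 3.02 at the sizing value, against a critical t of 2.018 on 42 df.

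| Two-group power | CSA | MyoKsyn | Rab27 |
|---|---|---|---|
| n=22, sizing values | 84% | 85% | 82% |
| n=22, pilot values | 44% | 34% | 60% |
| n=32, sizing values | 95% | 95% | 93% |
| n=32, pilot values | 59% | 46% | 77% |

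EV number has 89% at n=22 on either row.

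**Step 4: difference detectable with 80% power.** The detectable d is 0.865 at n=22 and 0.711 at n=32. Multiplying by the SDs:

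| | CSA | MyoKsyn | Rab27 |
|---|---|---|---|
| n=22 | 9.5 | 66 | 147 |
| n=32 | 7.8 | 54 | 121 |
| Pilot row | 6.1 | 36 | 116 |

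**Step 5: the sample sizes side by side.**
- SAP: 4 × 22 = 88
- Protocol, Study Design: 4 × 32 = 128; with 3 more per group for attrition, 4 × 35 = 140
- Protocol, subject population: 70
- Protocol, planned enrolment table: 2 × (3 + 9 + 2 + 56) = 140

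The Study Design and enrolment-table totals agree with each other. The SAP's 22 per group and the 70 subjects agree with neither.

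**The case against.** The best defence is that a planner may target a difference larger than a small pilot showed, that basing a figure on a pilot need not mean copying it, and that both rows are printed together, so nothing is hidden. Much of this stands. The effect sizes are computed correctly, and nothing in the documents shows that 10, 70 and 150 are wrong. What does not stand is the sentence itself: it gives the pilot as the basis for all the differences, and for three of them the step from pilot to planning value is missing.

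A second objection is that the pilot row may be a within-subject change, since only the next row is labelled as a difference of means. That is possible, and the 44/34/60% figures would then not apply. The derivation of 10, 70 and 150 would still be unshown.

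A third is that the main analysis is a two-way ANOVA, not a two-group test. If massage works equally in the suspended and weight-bearing groups, main-effect power at the pilot values (noncentrality d × √n, 4n − 4 df) is about 73% for CSA and 59% for MyoKsyn at n=22, and 88% and 76% at n=32. But the protocol's Background reports that unperturbed rat muscle showed no growth response to massage. With a zero effect in the weight-bearing groups, the same calculation gives 25% and 20% at n=22, and 34% and 26% at n=32. The ANOVA therefore does not rescue the claim unless its equal-effect assumption is stated and defended. The two-group figures match the SAP's own sizing calculation and its planned crossover t-test.

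Two stronger readings are tempting. One is that power is adequate only at the raised values. That overstates it: at n=22, 80% two-group power is reached from about 9.5 for CSA and 66 for MyoKsyn, slightly below 10 and 70. The other is that the 70 subjects are a per-gender count, because the enrolment table has 70 of each. The text does not say so.

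**Conclusion.** The stated basis is wrong as written for three of the four sizing outcomes. This rests on the SAP's own table and is certain. The choice of 22 per group follows from the raised values.

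The consequence for power is conditional. If the pilot row is a between-group difference, and with an inferred two-sided 5% test, the claim of enough power for muscle size and protein synthesis does not hold at the pilot values: about 44% for CSA and 34% for MyoKsyn at 22 per group. A two-group comparison at 32 per group still falls short (59% and 46%). If the pilot row is a within-subject change, no pilot-value power can be given.

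A reader might infer that the trial is underpowered or needs more participants. The documents do not support that. The raised differences may be defensible, and the true group size is unsettled. The fault is an unsupported statement of basis, an unlabelled row and an unreconciled n. It should be fixed.

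**What to change.** 1. **State the basis.** Say that the SDs and the EV-number difference came from the 6-subject pilot, and that the differences for CSA, MyoKsyn and Rab27 (10, 70, 150) were set above the pilot values (6.1, 36, 116), with the reason. Otherwise use the pilot values and restate the power. Label the pilot row as a between-group difference or a within-subject change.
2. **Replace the general power claim.** State alpha, sidedness and target power, then the differences detectable with 80% power in a two-group, two-sided 5% comparison: about 9.5 (CSA), 66 (MyoKsyn) and 147 (Rab27) at 22 per group, or 7.8, 54 and 121 at 32 per group. If the pilot row is a between-group difference, note that all of these exceed the pilot values. Give any ANOVA main-effect figure only with its equal-effect assumption stated, in view of the rat data.
3. **Reconcile the sample size** across the SAP (22 per group), the protocol's Study Design (32 per group, 128 enrolled, 140 recruited), its subject population text (70; say whether this is a total) and its planned enrolment table (140). Give the figures in item 2 at the reconciled n.

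The cost is two SAP sentences, one row label and consistent numbers in four places, with no added participants. The downside is that the stated power becomes less favourable.

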Deuterium oxide heavy water ($2H_2O$) is a stable, non-radioactive isotope that is indistinguishable from normal water. It is simply water that has a higher amount of a natural, but less abundant, form of hydrogen. Subjects will be required to ingest the heavy water for 9 days. (99% D_2O , Cambridge Isotope Laboratories). A target of 1-2% enrichment is achieved during a one week priming stage and maintained for the remainder of the study. Subjects will be sent home with 50 mL doses of heavy water in sealed sterile vials. The first two days, they will consume one 50 mL vial of the heavy water three times a day (150mL/day). The next 7 days, they will consume one 50 mL vial twice a day (100mL/day). This will total 1000mL of water per subject. Over the course of the 9 day trial, the subjects' blood will be drawn on day 2, 5, 7, and 9.

Blood Draws:

Blood samples will be obtained for protein synthesis measures and for the assessment of exosomes and circulating miRNAs. Left over blood will be stored in the lab indefinitely. Approximately 5-25 ml will be drawn.

Immobilization:

Participants of the immobilization/massage and immobilization/no massage groups will be placed in a knee immobilizer on their left leg and crutches, and will be non-weight-bearing starting on day 2 (after the first two days of heavy water intake) of the 9 day trial for a total of 7 days. The participants will be required to log and explain on the attached Immobilization Time Log any time they did not use/wear the crutches or knee immobilizer in order to track compliance.

Massage:

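### The SAP does not say which blood draw supplies EV number or what its % change is relative to, and its two-way ANOVA does not adjust for the pre-massage day-2 value

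*SAP*

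**What the plan says.** The SAP (Statistical Design and Power) sizes the study on four outcomes: "We used 4 main outcomes to determine sample size: cross sectional area (CSA), myofibrillar protein synthesis (MyoKsyn), extracellular vesicle (EV) number and mRNA levels of" one gene, Rab27. Its table is headed % change. For EV number it gives an expected difference of 0.29, a standard deviation of 0.294, an effect size of 0.99 and 18 per group; 22 per group is then chosen for the study. The group analysis is one sentence: "To determine statistically significant differences between the groups we will use a Two Way ANOVA to determine effects of ULLS and massage". Holm-Sidak tests follow a significant ANOVA, and a separate unpaired t-test addresses the crossover effect. No day term, baseline covariate or EV time point is named.

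The protocol's Blood Draws paragraph (Research Procedures) says "Blood samples will be obtained for protein synthesis measures and for the assessment of exosomes and circulating miRNAs". Study Design says "3-4 blood draws will be taken on days 2, 5, 7, and 9", and the Heavy Water paragraph repeats that "blood will be drawn on day 2, 5, 7, and 9". The weight-bearing groups also "drink deuterium oxide heavy water over 9 days which is associated with 3-4 blood draws". On timing, Study Design says "Massage treatments will begin on day 3", so the day-2 draw comes before any massage. Bracing of the unloaded groups also starts on day 2. Study Design gives the weight-bearing control group (WB-C) a biopsy on day 9 only.

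**The concern.** If EV number is the blood exosome measure, a pre-massage value is planned in every group. The muscle outcomes differ here, because WB-C has no day-2 biopsy. The SAP does not commit to using that value. As written, the ANOVA could be run on the day-9 value alone, on a percentage change from day 2, or on some other summary of the draws. These choices differ in precision, and leaving the choice open on a main outcome allows it to be made after the data are seen.

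What is at stake is efficiency and a defined analysis variable. An unadjusted day-9 analysis makes no use of the day-2 information. A change score uses it but carries the full noise of the baseline measurement into the outcome. Neither is as precise as regression adjustment for day 2, which also corrects for chance differences in starting EV number between groups.

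**Working it through.** **Inputs.** From the SAP: EV difference 0.29, standard deviation 0.294, n = 22 per group. Significance level, sidedness and power are not stated; I assume 0.05, two-sided, 0.80. The correlation r between EV values on two days is not given; I assume 0.5, with a range of 0.3 to 0.7, and equal variances on both days.

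**Reproducing the SAP's sizes.** A two-sample t-test on one value per person, using each difference divided by its standard deviation, requires:

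| Outcome | Effect size | n at 80% power | SAP |
|---|---|---|---|
| EV number | 0.29/0.294 = 0.986 | 17.15 → 18 | 18 |
| CSA | 10/11 = 0.909 | 20.00 → 20-21 | 21 |
| MyoKsyn | 70/76 = 0.921 | 19.51 → 20 | 19 |
| Rab27 mRNA | 150/170 = 0.882 | 21.17 → 22 | 22 |

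The stated sizes fit a comparison of one value per person at about 80% power.

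**Variance of the group comparison**, in units of the variance of a single EV value:
- day 9 only: 1
- change from day 2: 2(1 − r)
- day 9 adjusted for day 2 (ANCOVA): 1 − r²

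| r | ANCOVA / day 9 only = 1 − r² | ANCOVA / change = (1 + r)/2 |
|---|---|---|
| 0.3 | 0.91 | 0.65 |
| 0.5 | 0.75 | 0.75 |
| 0.7 | 0.51 | 0.85 |

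**Power, 22 versus 22.** The noncentrality is (0.986/√k) × √(22/2), with 42 degrees of freedom, where k is the variance ratio. The one degree of freedom spent on the covariate is ignored.
- Unadjusted, k = 1: noncentrality 0.986 × 3.317 = 3.27, power 0.89.
- k = 0.75: 3.27/0.866 = 3.78, power 0.96.
- If 0.294 is the standard deviation of a single value, k = 0.91, 0.75, 0.51 gives 0.92, 0.96, 0.99.
- If 0.294 is already the standard deviation of a change, k = 0.65, 0.75, 0.85 gives 0.98, 0.96, 0.93.

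Over both readings and the whole range of r, adjusted power lies between 0.92 and 0.99. These figures are for a single contrast at 0.05, before any Holm-Sidak adjustment.

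**Pooled massage main effect.** With two groups on each side this is 44 versus 44. At an effect size of 0.99, assumed equal with and without unloading, power is already about 0.996. Adjustment at r = 0.5 takes it to 0.9996.

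**The case against.** The best defence is that a two-way ANOVA on one value per person is valid, that EV number needs only 18 per group by the SAP's own table, and that Rab27 drives the sample size. All of that stands. At the protocol's 32 per group, the unadjusted contrast would already have power of about 0.97. The size of the gain also rests on a correlation that the documents do not give.

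Four stronger readings are tempting, and the documents do not support them.

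- *EV number is measured at all four draws in every group.* The protocol gives the draw days but no EV assay days, shares the blood with protein synthesis and miRNA work, and puts the count at three to four draws. That EV number comes from blood at all is a reasonable inference from the exosome sentence; the SAP does not state it.
- *The plan throws the baseline away.* The sample-size table is headed % change and includes EV number. If that change is from day 2, the baseline is used, though less efficiently. The reference is undefined, so neither reading is established.
- *Using every draw would bring a far larger gain.* That requires averaging days 5, 7 and 9 under an effect that is constant over time. Massage is given on days 3, 5, 7 and 9, so the effect may build. At r = 0.5 the adjusted three-day mean has variance (1 + 2r)/3 − r² = 5/12. If the effect grows as 1/3, 2/3, 1, its mean is 2/3 of the day-9 effect and power at 22 per group is 91%. If it grows as 0, 1/2, 1, the mean is half and power is 70%. Both are below the 96% of day-9 ANCOVA.
- *Repeat draws would be entered as independent observations, inflating the error rate.* Nothing in the SAP proposes this.

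**Conclusion.** The point holds as an under-specification with a free improvement attached. The SAP should say which draw defines EV number and what the % change refers to, and it should adjust for day 2. For a 22-versus-22 contrast, such as massage against sham within the unloaded groups, the expected gain is power of about 0.96 instead of 0.89. This rests on the SAP's effect size, an assumed r of 0.5 and an EV assay on both day 2 and day 9. For the pooled massage effect the gain is too small to matter.

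One caution applies to the unloading effect. Bracing starts on day 2, so the day-2 value is a clean baseline for that factor only if the blood is drawn before the brace goes on, and the protocol does not give the order.

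**What to change.** In the SAP's Statistical Design and Power section:

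1. State which draws are assayed for EV number, and define the reference for the % change in the table.
2. Analyse day-9 EV number with a two-way ANCOVA (ULLS, massage and their interaction) with the day-2 EV value as covariate, in place of an unadjusted day-9 value or a % change.
3. If days 5 and 7 are also assayed, use a mixed model with day and day-by-group terms and the day-2 value as covariate, and name the day-9 massage contrast as the comparison of interest. With complete data and an unstructured covariance this is essentially the day-9 ANCOVA; the extra draws mainly help when some day-9 values are missing.
4. Keep the two-way ANOVA for the muscle outcomes, because WB-C has no day-2 biopsy.
5. State in the protocol whether the day-2 blood is drawn before bracing.

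The cost is a few sentences of SAP and protocol text and a few lines of SAS. No participants or draws are added. If EV assays are not already planned on day 2, the cost also includes assaying blood that is already being drawn.

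### The two-way ANOVA leaves out sex, which is already recorded; adding it is a near-free improvement that would protect the non-concurrent ULLS contrast from one possible source of bias

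*SAP*

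**What the plan says.** - **Model.** SAP, Statistical Design and Power: "we will use a Two Way ANOVA to determine effects of ULLS and massage". Post hoc testing follows if the ANOVA is significant: "Holm Sidak posthoc tests will be performed in case significance is seen with the ANOVA". The crossover question is tested with an unpaired t-test. No covariate or stratification factor is named.
- **Sex.** The Protocol's Subject Demographics section admits either gender and plans 70 men and 70 women. Data Collection & Research Materials lists demographic information. The Participant Demographics table in the continuation review reports enrolment by gender in total, not by study group.
- **Order of enrolment.** Protocol, Study Design: "We will enroll the weight bearing groups after immobilization groups". Subject Demographics describes random assignment to all four groups.
- **Biopsies.** Protocol, Study Design: "Weight bearing control groups will only have one biopsy taken on day 9". The other three groups have a day-2 biopsy from the right leg.
- **Outcome scale.** The SAP's sample-size table is headed as % change for EV number, CSA, MyoKsyn and Rab27 mRNA.

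**The concern.** In a trial randomised concurrently to all four groups, leaving out a prognostic factor costs only precision. Two features make this trial different.

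First, if the ULLS groups are filled before the weight-bearing groups, the ULLS factor compares people recruited at different times. Any drift in the sex mix over that time enters the ULLS effect and its interaction with massage.

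Second, the usual reassurance is that a within-person change cancels stable differences between the sexes. It is not available for every group here. The weight-bearing control group (WB-C) has no earlier biopsy, so biopsy outcomes such as CSA and muscle mRNA must enter as day-9 levels for that group, with any sex difference left in. EV number is better placed: the Protocol draws blood for exosomes and lists day 2 among the draw days, so an early value may exist.

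At stake are some precision in pairwise contrasts and one avoidable route to bias in the ULLS contrast.

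**Working it through.** **Inputs.** From the SAP table: "Expected μ₁-μ₂ 0.29 10 70 150"; "Standard Deviation, σ 0.294 11 76 170"; "n per Group 18 21 19 22". The chosen size is 22 per group. The Protocol gives other totals elsewhere (32 per group in Study Design, 70 subjects in Subject Demographics); the SAP's 22 is used here. Alpha and target power are not stated; two-sided 0.05 and 80% are assumed, without multiplicity adjustment.

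**1. The plan's own sample sizes.** For a two-sample t-test with d = expected difference / SD, the smallest n per group giving 80% power (noncentral t) is:

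| Outcome | d | Recomputed n | SAP n |
|---|---|---|---|
| EV number | 0.29/0.294 = 0.99 | 18 | 18 |
| CSA | 10/11 = 0.91 | 21 | 21 |
| MyoKsyn | 70/76 = 0.92 | 20 | 19 |
| Rab27 mRNA | 150/170 = 0.88 | 22 | 22 |

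The plan's figures reproduce to within one participant, so the assumed alpha and power fit. The calculation is pairwise and has no sex term.

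**2. Enrolment counts.** Women: 1 + 3 + 3 + 26 + 1 = 34. Men: 2 + 12 + 1 = 15. Share of women: 34/49 = 69%.

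**3. Precision, pairwise contrast (Rab27, 22 v 22).** Noncentrality = d × √(n/2) = 0.882 × √11 = 2.93. Power is 81.6% with 42 df (two groups alone) and 82.5% with 84 df (four-group ANOVA error). With sex in the model, if it explains a share R² of the variance, noncentrality is divided by √(1 − R²) and one df is lost (83 df):

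| Assumed R² | Power |
|---|---|
| no sex term | 82.5% |
| 5% | 84.3% |
| 10% | 86.2% |
| 20% | 89.9% |

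To link R² to a sex gap of g SD at the observed split: R² = 0.694 × 0.306 × g² = 0.212 g². Gaps of 0.2, 0.5 and 0.8 SD give R² of about 0.9%, 5.3% and 13.6%, and power gains of roughly 0.3, 2 and 5 percentage points.

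**4. Precision, main effects (44 v 44).** If the same d = 0.88 holds as a main effect without interaction, noncentrality = 0.882 × √22 = 4.14 and power is about 98% without a sex term. There is little left to gain.

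**5. Bias in the ULLS main effect (44 v 44).** Shift = (difference in share of women between ULLS and weight-bearing) × (sex gap in SD). Type I error is the two-sided rejection rate at noncentrality shift × √22. All inputs are assumed:

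| Imbalance | Sex gap | Shift | Shift / 0.88 | Type I error |
|---|---|---|---|---|
| 10 points | 0.2 SD | 0.02 SD | 2% | 5.1% |
| 20 points | 0.5 SD | 0.10 SD | 11% | 7.5% |
| 30 points | 0.8 SD | 0.24 SD | 27% | 20% |
| 0 points, or no sex gap | – | 0 | 0% | 5% |

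**6. Price of adjusting when sex does not matter.** One df, plus variance inflation of 1/(1 − r²) for the ULLS contrast, where r² = imbalance² × 0.25 / 0.212. At 20 points this is 1.05; at 30 points, 1.12. With balanced groups it is 1.

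**The case against.** **No sex effect and no sex-by-group counts are given.** This stands. A reader might infer from the omission that power is lost; the documents do not show it, and for gaps up to about 0.5 SD the pairwise gain is only about 2 points.

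**34:15 does not show imbalance between groups.** This also stands. A reader might take the departure from the planned 70:70 as evidence of bias, but a 69% share of women is compatible with the same mix in every group, and the planned split is a demographic projection, not a design constraint. The 49 may not even all belong to the four-group trial: a 40-person device-reliability study sits under the same application, and the attached latest consent files are numbered 38 and 39.

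**Chance imbalance is not bias.** Correct. One standard error of the difference in sex mix at 44 v 44 is √(2 × 0.694 × 0.306/44) = 0.098, about 10 points, but chance imbalance averages to zero and its variance is already in the error term. Only systematic drift between recruitment periods biases the contrast, and the documents give no estimate of it.

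**Massage and crossover comparisons.** A reader might extend the worry to these. If massage is randomised within each loading condition, the massage contrasts and U-M versus U-C are unbiased in expectation with or without sex.

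**A sex term misses the larger problem.** Partly right. Sequential enrolment exposes the ULLS contrast to anything that changes over time, and sex is one such factor. That limits the remedy without making it worthless.

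**Conclusion.** The point holds as a low-cost improvement, between optional and recommended, and not as a demonstrated error. The supported facts are the omission of a recorded variable from the model, enrolment of the weight-bearing groups after the ULLS groups, and the absence of a baseline biopsy in WB-C. Together they leave the ULLS contrast without protection by design against a shift in sex mix, most clearly for CSA and muscle mRNA.

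The size depends on two quantities the documents do not give: the effect of sex on each outcome and the sex mix by group. Under the assumed ranges, the pairwise gain runs from negligible to about 7 points, main effects gain little, and the bias runs from zero to 0.24 SD. The documents do not support saying that power has been lost, that the groups are imbalanced, or that the massage or crossover results are biased.

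**What to change.** 1. In the SAP, pre-specify sex as a fixed effect in the ANOVA for all four main outcomes. Do this before the data are examined, since adding it afterwards would be open to challenge.
2. Report sex by group with the baseline characteristics, for participants in the four-group trial only.
3. Optionally, replace the unpaired crossover t-test with a linear model containing group and sex. The reason is precision only.
4. Reconcile the Protocol's Subject Demographics section (random assignment to four groups) with Study Design (weight-bearing groups enrolled later). If enrolment is sequential, state that ULLS contrasts are non-concurrent and that sex adjustment is only a partial remedy.
5. State how each outcome is defined for WB-C, where no earlier biopsy exists.

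The sex term costs SAP wording and one degree of freedom, plus the small variance inflation shown above if the groups turn out unbalanced. No new data are needed.
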